4.0 Test Schedule

All routine assessments must be performed within ± 7 days of the day indicated on the Visit Schedule.

Tests and procedures	Pre-Treatment	Active Treatment					
	≤ 7 days prior to registration*	Cycle 1, Day 1	Cycle 1, Day 8	Cycle 1 Day 21	Cycles 2 and above, Day 1	Cycles 2 and above, Day 8 ⁷	Early Discontinuation or End of Treatment
History and exam, weight, vitals, PS	X	X			X	X	X
Height	X						
Adverse event assessment	X	X			X		X
BM testing ²	X				X ²		X
Biomarkers FLT3 Mutation by PCR	X						X
Pregnancy Test	X						
Hematology group(CBC) Hgb, , PLT, WBC with diff. ¹	X	X ¹	X	X	X ¹	X	X
Serum Chemistry (magnesium, potassium, phosphorus, total bilirubin, direct bilirubin ⁵ , alkaline phosphatase, AST, ALT, creatinine)	X	X	X	X	X	X	X
Serum Chemistry (Serum Amylase & Lipase)	X	X			X		X
MUGA/Echo	X						
LDH	X						
Urine analysis (proteinuria, hematuria) ^R	X						
ECG (QTcF results preferred) ^{R 3}	X		X			X ³	X
Patient Medication Diary (Appendix III ⁴)			X		X	X	
Research Correlatives ^{R, 6}	X		X		X ⁶		

* Labs done on the same day of consent but prior to consenting do not need to be repeated.

1. CBC will be done weekly for cycle 1-4. After cycle 4, to be performed Day 1 and Day 8.
2. Bone marrow (BM) sampling will be done upon screening, and day 1 of cycle 3, 5, 9 and then as clinically needed. Recent bone marrow within 21 days (even prior to consenting) will be acceptable and FLT3 PCR could be done on peripheral blood if blasts >10%. Outside FLT3

testing at bone marrow biopsy will be allowed and used if done.

3. ECGs will be performed locally at screening, Day 8 (prior to dosing) of each cycle, and when there's any dose change due to QTc prolongation or re-initiation after a dose interruption. When a dose change occurs due to QTc prolongation or upon re-starting midostaurin, an ECG must be obtained at 7 days afterwards. QTcF results are preferred, however all reporting methods will be accepted.
 4. The diary must begin the day the patient starts taking midostaurin and must be completed per protocol and returned to the treating institution OR compliance must be documented in the medical record by any member of the care team. Patients will be asked to return all unused medication at each visit.
 5. Get direct bilirubin if total bilirubin > upper normal limit.
 6. Correlatives for blood and bone marrow. See section 14.

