- IRB approval at the registering institution
 - Patient eligibility
 - Existence of a signed consent form

- Existence of a signed authorization for use and disclosure of protected health information
- 6.5 At the time of registration, the following will be recorded:
- Patient has/has not given permission to store and use his/her sample(s) for future research of AML at Mayo.
 - Patient has/has not given permission to store and use his/her sample(s) for future research to learn, prevent, or treat other health problems.
 - Patient has/has not given permission for MCCC to give his/her sample(s) to researchers at other institutions.
- 6.6 Treatment cannot begin prior to registration and must begin ≤ 7 days after registration.
- 6.7 Pretreatment tests/procedures (see Section 4.0) must be completed within the guidelines specified on the test schedule.
- 6.8 All required baseline symptoms (see Section 10.5) must be documented and graded.
- 6.9a Treatment on this protocol must commence at Mayo Clinic Rochester under the supervision of a hematologist.
- 6.9b Study drug is available on site.

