7.0 Protocol Treatment

7.1 Treatment Schedule

- 7.11 Patients eligible for the study based on screening tests will be enrolled on the study.
- Patients will proceed to next cycle every 28 days (or later) based on investigator opinion when reviewing each case based on hematological and physical findings.
 - Patients who tolerate combination therapy well and fail to achieve CR/CRi/PR/morphologic leukemia-free state by end of cycle 2, could get midostaurin on days 1-28 of each subsequent cycle, rather than just days 8-21, as per treating MD decision.
 - Patients who achieve a CR/CRi/PR/morphologic leukemia-free state by end of cycle 8 will continue on current regimen.
 - Patients who fail to achieve a CR/CRi/PR/ morphologic leukemia-free state in bone marrow blasts by end of cycle 8 will go to event monitoring.
 - Patients will get a repeat bone marrow biopsy on day one of cycles 3, 5, 9 and then as clinically indicated (see Test Schedule, section 4.0). Patients who achieve CR/CRi will not need repeat bone marrow assessment unless deemed necessary by investigator.
 - Hydroxyurea and/or leukocytapheresis use is allowed to control rising blasts as deemed necessary by treating investigator at any

time.

Cycle length = 28 days (+/- 7 days)

Agent	Dose	Route	Day	Comments
Decitabine ¹	20 mg/m ²	IV	1-5	Could be given days 2-5 by local MD (outside Mayo Clinic).
Midostaurin ²	50 mg twice/day	Oral	8-21	Midostaurin could be given continuously (day 1-28) starting cycle 3 based on MD decision (see 7.11).

1. May be held as per treating physician judgment.
2. If decitabine is held, then midostaurin will be held. If decitabine is administered, midostaurin cannot be held, but can be omitted.

7.12 Maximum cycles of midostaurin are 18, after which a discussion with Novartis will be done on a per patient basis whether to keep patient on continued therapy with the combination of decitabine and midostaurin on study (continue active monitoring per section 4.0).

7.13 If midostaurin is discontinued, single agent Decitabine may be given beyond cycle 18 off protocol until relapse or disease progression off protocol. The patient will go to event monitoring per section 18.0

Note: If single agent Decitabine is being given off protocol, the end of active treatment form should be filled out at the end of cycle 18. Reason treatment ended should be reported as treatment completed per protocol criteria.

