11.0 Treatment Evaluation

11.1 Complete hematologic response (CR)

Less than 5% blasts in a non-hypocellular marrow with a granulocyte count ≥ 1.0 , and a platelets count ≥ 100 with complete resolution of any extramedullary disease and absence of peripheral blood blasts. The patient is in sustained CR if they have previously achieved a CR and continue to meet the CR criteria (at least 28 days).

CR incomplete (CR_i) is called if patient meets all CR criteria except for residual neutropenia (ANC < $1 \times 10^9/L$) or thrombocytopenia (platelets < $100 \times 10^9/L$)

- 11.11 Complete cytogenetic remission (CCyR)
The absence of chromosome abnormalities (if present at diagnosis) on conventional cytogenetic study using G-banding (at least 10 metaphases present).
- 11.12 Complete molecular remission (CMR)
The achievement of negative PCR for FLT3 mutation (if done and if present at diagnosis).
- 11.13 MRD: Minimal Residual Disease
Positive PCR for FLT3 mutation or flow cytometry for FLT3 overexpression from peripheral blood or bone marrow.
- 11.2 Morphologic leukemia-free state (MLFS):
If bone marrow blasts <5%, absence of Auer rods blasts, absence of extramedullary disease without hematological recovery.
- 11.3 Partial response (PR)
The presence of trilineage hematopoiesis in the bone marrow with recovery of ANC and platelet count to above levels, but with 5-25% bone marrow blasts and $\geq 50\%$ decrease in bone marrow blast percentage from baseline.
- 11.4 No response (NR)
Failure to achieve a PR, MLFS, CRi, or CR.
- 11.5 Relapse:
Disease recurrence after achieving CR. Disease recurrence is defined by blast $\geq 5\%$ in the bone marrow, or recurrence of peripheral blood blasts or extramedullary involvement.
- 11.6 Treatment failure:
Resistant disease: Failure to achieve CR/CRi/PR/morphologic leukemia-free state by the end of 8 cycles of induction .

Note: These patients will be recorded as an objective status of NR to document depth of response but will be considered treatment failures at the time of analysis.

Death in aplasia: Death occurring ≥ 7 days following completion of treatment with aplastic/hypoplastic bone marrow (obtained within 7 days of death) with no evidence of persistent leukemia

Death from indeterminate cause: Death occurring during therapy or < 7 days following treatment completion, or ≥ 7 days following completion of treatment with no blast in the blood but no bone marrow examination available

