13.0 Treatment/Follow-up Decision at Evaluation of Patient

13.1 Criteria for Patient Initiation of Event Monitoring:

- Delay > 28 days for the next cycle (due to non-hematological drug toxicity)
- Disease relapse
- Failure to achieve CR or CRi or PR or MLFS by end of cycle 8
- Patient withdraws consent to continue in the trial
- Patient develops an intercurrent illness that precludes further participation
- The Investigator withdraws the patient in the patient's best interests
- Administrative reasons (e.g., the patient is transferred to hospice care)
- An adverse event, which in the opinion of the Investigator precludes further trial participation
- Patient discontinues either the Decitabine or the Midostaurin in the maximum 18 cycles.

All attempts should be made to complete the End of Study procedures if a patient withdraws from the trial early. The patient will go to the event-monitoring phase per Section 18.0.

- 13.2 Patients who achieve and sustain a CR/CRi/PR/MLFS by end of cycle 8, will receive a maximum total of 18 cycles of treatment. After 18 cycles, the patient will go to event monitoring, unless they are continuing the combination of midostaurin and decitabine beyond 18 cycles per section 7.12.
- 13.3 Event monitoring: Patients who are alive will be followed in event monitoring every 6 months until death or up to 2 years from registration.
- 13.4 A patient is deemed *ineligible* if after registration, it is determined that at the time of registration, the patient did not satisfy each and every eligibility criteria for study entry. The patient may continue treatment off-protocol at the discretion of the physician as long as there are no safety concerns, and the patient was properly registered. The patient will go directly to the event-monitoring phase of the study (or off study, if applicable).
 - If the patient received treatment, all data up until the point of confirmation of ineligibility must be submitted. Event monitoring will be required per Section 18.0 of the protocol.
 - If the patient never received treatment, on-study material and the End of Active Treatment/Cancel Notification Form must be submitted. No further data submission is necessary.

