- 16.23 Accrual Rate and Study Duration: The anticipated accrual rate is 1 evaluable patient per month. Therefore, the accrual period is expected to be approximately 2 years. The primary endpoint will be evaluated approximately 2.75 years after the trial opens, or after the last patient accrued has been observed for at least 6 months. The total study duration is expected to be approximately 3 years.
- 16.24 Power and Significance Level: Assuming that the number of successes is binomially distributed, the significance level is .09, i.e. there is a 9% chance of finding the drug to be effective when it truly is not. The probability of declaring that this regimen warrants further study (i.e. statistical power) under various success proportions can be tabulated as a function of the true success proportion as shown in the following table.

If the true success proportion is...	0.10	0.15	0.20	0.25	0.30
Then the probability of declaring that the regimen warrants further study is...	0.09	0.29	0.54	0.75	0.89

- 16.25 Other considerations: Adverse events, quality/duration of response, and patterns of treatment failure observed in this study, as well as scientific discoveries or changes in standard care will be taken into account in any decision to terminate the study

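### Section 16.23 allows the primary read-out when the last patient has 6 months of observation, before the last scheduled response marrow (Cycle 9 Day 1, nominally 7.4 months); the effect is small and conservative

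*Combined protocol and SAP*

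**What the plan says.** Section 16.23 gives two times for the primary evaluation and joins them with an open conjunction: "evaluated approximately 2.75 years after the trial opens, or after the last patient accrued has been observed for at least 6 months". It does not say which governs. It expects 1 evaluable patient per month, about 2 years of accrual and a total duration of about 3 years. Section 16.5 defines the Primary Endpoint Completion Date by the same 6-month follow-up and dates it at 2.5 years, for results-reporting purposes.

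On assessments, Section 7.11 states "Patients will get a repeat bone marrow biopsy on day one of cycles 3, 5, 9", and the Section 4.0 footnote agrees: "day 1 of cycle 3, 5, 9 and then as clinically needed". Section 7.11 also says "Patients who achieve CR/CRi will not need repeat bone marrow assessment unless deemed necessary by investigator". The treatment table gives "Cycle length = 28 days (+/- 7 days"), while the text of 7.11 speaks of 28 days or later. The Schema lets each next cycle be delayed by up to 28 days.

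Success is CR or CRi as the objective status during therapy (16.11). The proportion uses all evaluable patients as its denominator (16.312). The decision turns on 4 or fewer versus 5 or more successes in the first 24 (16.211). Section 16.324 contemplates comparing patients who first reach CR/CRi at 2 months with those who first reach it at 8 months.

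**The concern.** CR and CRi both require a marrow result. A patient not in CR/CRi at the Cycle 5 marrow has no further scheduled opportunity to be documented until Cycle 9. If the 6-month alternative were used, the last enrollees would be judged before that assessment, while earlier patients would have had it. The plan itself foresees first responses at 8 months. It has no rule for a patient who is on treatment and awaiting the Cycle 9 marrow at the cut, so under 16.312 that patient simply stays in the denominator without a success.

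The decision is a hard count, so one undocumented responder can turn 5 successes into 4. The open conjunction also leaves the analysis date to choice.

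**Working it through.** **Inputs.** n = 24, success threshold 5, rates 10% and 30% (16.21, 16.211); 1 patient per month, so enrolment at months 1 to 24 (16.23); marrows on Day 1 of Cycles 3, 5 and 9 (4.0, 7.11); cycles of 28 days, 35 days (upper end of the table's range) or 56 days (28 plus the Schema's maximum delay every time); 1 month = 30.44 days.

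**The plan's own figures.** P(X ≥ 5) for a binomial with n = 24 is 0.0851 at 10%, then 0.287, 0.540, 0.753 and 0.889 at 15%, 20%, 25% and 30%. These match the stated 0.09, 0.29, 0.54, 0.75 and 0.89.

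**When the marrows fall.** Cycle c Day 1 is (c − 1) × cycle length from the start of treatment.

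| Cycle length | Cycle 5 Day 1 | Cycle 9 Day 1 |
|---|---|---|
| 28 days | 112 d = 3.7 months | 224 d = 7.4 months |
| 35 days | 140 d = 4.6 months | 280 d = 9.2 months |
| 56 days (extreme) | 224 d = 7.4 months | 448 d = 14.7 months |

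Section 6.6 allows treatment to start up to 7 days after registration. That moves Cycle 9 Day 1 to 231 d (7.6 months) or 287 d (9.4 months) from registration and changes none of the counts below. For Cycle 9 Day 1 to fall within 6 months, cycles would have to average under 6 × 30.44 / 8 = 22.8 days. With the 7-day assessment window of Section 4.0 used early, the figure is (182.6 + 7) / 8 = 23.7 days.

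**Patients short of Cycle 9 Day 1** (cut month − enrolment month < time of that marrow):

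| Cut | 28-day | 35-day | 56-day |
|---|---|---|---|
| Month 30 (24 + 6) | 2 | 4 | 9 |
| Month 33 (2.75 years) | 0 | 1 | 6 |

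No one is short of the Cycle 5 marrow at month 30 on 28- or 35-day cycles. On 56-day cycles 2 of the 9 are. If 26 patients are accrued, the 6-month cut moves to month 32, and 0 (28-day) or 2 (35-day) of the first 24 are short.

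**Effect on the decision.** Let k patients be short and f be the share of responders first documented at Cycle 9. The documents give no value for f; I assume 10% to 30%. Then X = Bin(24 − k, p) + Bin(k, p(1 − f)), and the expected number of missed successes is k × p × f.

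| k | Missed successes, p = 0.30 | P(X ≥ 5), p = 0.30 | P(X ≥ 5), p = 0.10 |
|---|---|---|---|
| 0 | 0 | 0.889 | 0.085 |
| 2 | 0.06 to 0.18 | 0.884 to 0.874 | 0.083 to 0.078 |
| 4 | 0.12 to 0.36 | 0.879 to 0.857 | 0.080 to 0.071 |

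The power loss is 0.5 to 1.5 points for k = 2 and 1.0 to 3.2 points for k = 4. I give no power for the 56-day case. Two of those patients also miss Cycle 5, which would need a further unsupported assumption.

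**The case against.** The strongest reply is that the planned date already deals with this. At 2.75 years with 24 months of accrual the last patient has 33 − 24 = 9 months, past Cycle 9 Day 1 on 28-day cycles. Six months is a stated minimum, so harm requires reading out about 3 months before the planned date. Only late enrollees still on treatment without CR/CRi after two marrows are exposed, and a marrow done on clinical grounds could still catch a response. All of this stands, and it is why the point is minor. It does not remove the permission: under planned accrual the 6-month condition is met at month 30, and nothing says the later date applies. Nor does the 2.75-year date protect fully once permitted cycle delays are considered.

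Four stronger readings are tempting but not supported:

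- **That 16.23 and 16.5 contradict each other.** The dates differ (2.75 against 2.5 years) without explanation, but 16.5 concerns registry timing. That is not a proven contradiction.
- **That the cut conflicts with the resistant-disease definition in 11.6**, "Failure to achieve CR/CRi/PR/morphologic leukemia-free state by the end of 8 cycles of induction". That definition includes PR and morphologic leukemia-free state. It is not the primary success criterion and does not settle when a patient counts as a non-success.
- **That the false-positive risk rises.** Missing a late response can only lower the count.
- **That the open conjunction is the whole problem, with 35-day cycles as the worst case.** The Schema's delays show that neither is true.

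**Conclusion.** The concern holds as a minor design point. Section 16.23 permits a primary read-out about 1.4 months (28-day cycles) or 3.2 months (35-day cycles) before the last enrollee's final scheduled response marrow, with no rule for patients caught in between. On those cycle lengths it affects 2 to 4 of 24 patients and costs about 0.5 to 3.2 points of power at a 30% rate, with a lower type I error.

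The size rests on steady accrual of one per month, a cut at exactly month 30, and an assumed 10-30% share of responders first documented at Cycle 9. The counts are not upper limits. The 56-day case is extreme, since it needs the maximum delay in every cycle, but the text allows it.

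**What to change.** In 16.23, replace the 6-month alternative with wording such as:

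> The primary endpoint will be evaluated when each of the first 24 evaluable patients has achieved CR/CRi, has completed the Cycle 9 Day 1 response assessment, or has left treatment (estimated at about 2.75 years), and no later than 3 years after the trial opens. Any patient still awaiting that assessment at that limit is counted as a non-success, and the number of such patients is reported.

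The CR/CRi clause is needed because 7.11 exempts those patients from repeat marrows. In 16.5, align the Primary Endpoint Completion Date with this trigger or state how the two relate. Keep success defined as occurring during therapy, and report CR/CRi first seen after the primary analysis as an update.

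**Cost.** One sentence and a cross-reference, with no change to endpoint, sample size or decision rule. If the last patient has to be followed to Cycle 9, the read-out comes at 24 + 7.4 = 31.4 months (2.61 years) or 24 + 9.2 = 33.2 months (2.77 years), against 30 months under the 6-month trigger. It is earlier if the last patients are already in CR/CRi or off treatment, and later with permitted delays. Without the cap the extreme case is 24 + 14.7 = 38.7 months (3.2 years), beyond the stated total duration; that is the reason for the cap. In that extreme case the cap would leave 3 patients (enrolled in months 22 to 24, with 14 to 12 months of observation) counted as non-successes and reported.

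The change equalises scheduled assessments through Cycle 9 only, apart from any patient caught by the cap. Responders "will receive a maximum total of 18 cycles of treatment" (18 × 28 = 504 days, 16.6 months), so observation windows after Cycle 9 remain unequal.

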16.3 Analysis Plan

16.31 Primary Outcome Analyses:

16.311 Definition: The primary endpoint of this trial is the proportion of complete responses to therapy. A success is defined as a CR or CRi as the objective status. All patients meeting the eligibility criteria who have signed a consent form and have begun treatment will be evaluable for complete response.

16.312 Estimation: The proportion of successes will be estimated by the number of successes divided by the total number of evaluable patients. Exact binomial confidence intervals for the true success proportion will be calculated.

16.32 Secondary Outcome Analyses:

- 16.321 Overall survival time is defined as the time from registration to death due to any cause. The distribution of overall survival will be estimated using the method of Kaplan-Meier {Kaplan E, 1958 #831}. In addition, the overall survival rate at 1 year after registration will be reported.
- 16.322 Progression-free survival time is defined for all evaluable patients as the time from registration to the time of relapse or death due to any cause. The distribution of progression-free survival will be estimated using the method of Kaplan-Meier. In addition, the progression-free survival rate at 1 year after registration will be reported.
- 16.323 The overall response rate will be estimated by the total number of complete or partial responses (CR, CRi, MLFS, or PR) divided by the total number of evaluable patients. All evaluable patients will be used for this analysis. Exact binomial 95% confidence intervals for the true overall response rate will be calculated.
- 16.324 Duration of complete response is defined for all evaluable patients who have achieved a CR or CRi as the date at which the patient's objective status is first noted to be a CR or CRi to the earliest date relapse is documented. The distribution of duration of complete response will be estimated using the method of Kaplan-Meier. If there are a sufficient number of CR/CRi, a landmark analyses may be performed to compare duration of CR/CRi in patients who first achieved a CR/CRi at 2 months vs those who first achieved a CR/CRi at 8 months.
- 16.325 Adverse Events: All eligible patients that have initiated treatment will be considered evaluable for assessing adverse event rate(s). The maximum grade for each type of adverse event will be recorded for each patient, and frequency tables will be reviewed to determine patterns. Additionally, the relationship of the adverse event(s) to the study treatment will be taken into consideration.

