16.0 Statistical Considerations and Methodology

16.1 Overview: This is a phase II study of a combination of midostaurin and decitabine in elderly patients with newly diagnosed AML and FLT3 mutation. This study will use a one-stage binomial design to assess the efficacy of this combination.

16.11 Endpoint: The primary endpoint in this trial is the proportion of complete responses during therapy. A success is defined as a CR or CRi as the objective status during therapy. Throughout Section 16.0, complete response will be considered synonymous with “success”, unless specified otherwise. All patients meeting the eligibility criteria who have signed a consent form and have begun treatment will be evaluable for response.

16.2 Statistical Design:

16.21 Decision Rule:

In previous studies of elderly AML patients treated with single agent decitabine as frontline therapy, complete response rates of 15%-24% were seen (Cashen, 2010 #813} {Lubbert, 2007 #812}). An improvement in complete response rate with the addition of midostaurin to decitabine would be of interest.

The largest success proportion where the proposed treatment regimen would be considered ineffective in this population is 10%, and the smallest success proportion that would warrant subsequent studies with the proposed regimen in this patient population is 30%. A one-stage binomial design uses 24 evaluable patients to test the null hypothesis that the true complete response rate is at most 10%.

16.211 Final Decision Rule: Enter 24 evaluable patients into the study. If 4 or fewer successes are observed in the first 24 evaluable patients, we will consider this regimen ineffective in this patient population. If 5 or more successes are observed in the first 24 evaluable patients, we may recommend further testing of this regimen in subsequent studies in this population.

- 16.212 Over Accrual: If more than the target number of patients are accrued, the additional patients will not be used to evaluate the stopping rule or used in any decision making process. Analyses involving over accrued patients are discussed in Section 16.34.
- 16.22 Sample Size: This study is expected to require 24 evaluable patients. We anticipate accruing 2 additional patients to account for ineligibility, cancellation, major treatment violation, or other reasons. Therefore, the study is expected to accrue a maximum of 26 patients overall.

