Accrual will be temporarily suspended to this study if at any time we observe events considered at least possibly related to study treatment (i.e. an adverse event with attribute specified as "possible," "probable," or "definite") that satisfy one of the following:

- if 4 or more patients in the first 12 treated patients experience a grade 4 or higher non-hematologic adverse event at least possibly related to treatment excluding infections and hypophosphatemia, hypocalcemia, hypo- or hyperkalemia, hyperuricemia as these abnormal lab results tend to resolve quickly (≤ 7 days) without affecting or jeopardizing patient safety.
- if after the first 12 patients have been treated, 30% of all patients experience a grade 4 or higher non-hematologic adverse event at least possibly related to treatment excluding infections and hypophosphatemia, hypocalcemia, hypo- or hyperkalemia,

hyperuricemia as these abnormal lab results tend to resolve quickly (≤ 7 days) without affecting or jeopardizing patient safety.

We note that we will review grade 4 and 5 adverse events deemed “unrelated” or “unlikely to be related”, to verify their attribution and to monitor the emergence of a previously unrecognized treatment-related adverse event.

16.5 Results Reporting on ClinicalTrials.gov: At study activation, this study will have been registered within the “ClinicalTrials.gov” website. The Primary and Secondary Endpoints along with other required information for this study will be reported on ClinicalTrials.gov. For purposes of timing of the Results Reporting, the initial estimated completion date for the Primary Endpoint of this study is 2.5 years after the study opens to accrual. The definition of “Primary Endpoint Completion Date” (PECD) for this study is at the time the last patient registered has been followed for at least 6 months.

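### Section 16.325 leaves treated patients later found ineligible out of the adverse-event rates, while the stopping rule in 16.42 has no such restriction

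*Combined protocol and SAP*

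**What the plan says.** The deciding sentence is in section 16.325: "All eligible patients that have initiated treatment will be considered evaluable for assessing adverse event rate(s". Eligibility is thus a condition for entering the adverse-event rates, as it is for response in 16.11 and 16.311 ("All patients meeting the eligibility criteria who have signed a consent form and have begun treatment will be evaluable for complete response").

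Section 13.4 calls a patient ineligible when, after registration, "it is determined that at the time of registration, the patient did not satisfy each and every eligibility criteria for study entry". It expects that some of these patients will already have been dosed: "If the patient received treatment, all data up until the point of confirmation of ineligibility must be submitted". They then move to event monitoring.

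The stopping rule in 16.42 is worded differently. Its first limb applies "if 4 or more patients in the first 12 treated patients experience a grade 4 or higher non-hematologic adverse event", and its second applies "if after the first 12 patients have been treated, 30% of all patients experience a grade 4 or higher non-hematologic adverse event". Neither limb mentions eligibility.

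Goal 2.24 is the safety and toxicity of the regimen. Section 16.22 plans 24 evaluable patients plus 2 for ineligibility, cancellation, major violation and other losses, 26 in all. No section puts treated ineligible patients back into the adverse-event tables or gives a reason for the two populations.

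**The concern.** Limiting the response set to eligible patients is a defensible choice when the question is whether the regimen works in the intended population. A toxicity rate asks a different question: what happened to the people who were exposed. That set is normally defined by receipt of drug, and a flaw in a patient's eligibility does not undo the exposure.

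Here the plan collects toxicity data from such patients and then leaves them out of the rates. In a trial of about two dozen patients, one or two can move a percentage visibly or decide whether an uncommon event is listed at all. Accrual could also be suspended on one set of patients while the final report describes another, and a reader could not reconcile the two.

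**Working it through.** **Inputs.** Planned evaluable patients 24, maximum accrual 26, allowance 2 (16.22). Response cut-off 5 of 24 (16.211), null rate 10% and target rate 30% (16.21). Stopping limits of 4 in the first 12 treated, then 30% (16.42).

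**The plan's own figures.** The exact binomial P(X ≥ 5 | n = 24) is 0.0851, 0.2866, 0.5401, 0.7534 and 0.8889 at true rates 0.10, 0.15, 0.20, 0.25 and 0.30. This agrees with the table in 16.24 (0.09, 0.29, 0.54, 0.75, 0.89). The response design is sound as stated, and this point does not touch it.

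**Effect on a reported rate.** Let N patients be treated and x of them have the event. Let k be later found ineligible, of whom e had the event.

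- Rate by exposure: x / N
- Rate under 16.325: (x − e) / (N − k)

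The 16.325 rate is the lower of the two only when e/k exceeds x/N.

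The documents do not say how many treated patients will be found ineligible. I assume 0 to 2, the upper end being the whole allowance. The event counts below are illustrations.

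With N = 26, x = 6 and k = 2, the exposure rate is 6/26 = 23.1%:

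| Excluded patients with the event (e) | Rate under 16.325 |
|---|---|
| 2 | 4/24 = 16.7% |
| 1 | 5/24 = 20.8% |
| 0 | 6/24 = 25.0% |

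For an uncommon event with x = 2, k = 2 and e = 2, 2/26 = 7.7% becomes 0/24, and the event is absent from the table.

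**Monitored against reported, for the same qualifying event.**

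- First limb: 4 of the first 12 treated (33.3%) suspends accrual. If one of the 12 is later found ineligible, the 16.325 rate in that cohort is 3/11 = 27.3% if that patient had the event and 4/11 = 36.4% if not.
- Second limb at 26 treated: 8/26 = 30.8% (exact 95% interval 14.3 to 51.8) meets the 30% limit. With two exclusions the reported rate is 6/24 = 25.0% (9.8 to 46.7), 7/24 = 29.2% (12.6 to 51.1) or 8/24 = 33.3% (15.6 to 55.3), according to whether 2, 1 or 0 of the excluded patients had the event.

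The second limb refers to all patients rather than all treated patients. On either reading it is not confined to eligible ones.

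**The case against.** The strongest reply is that very little is affected. Eligibility is checked before a registration is accepted (6.4), and the front matter rules out waivers. The allowance of 2 also covers cancellations, who by 13.6 never received treatment, so the realistic number of treated ineligible patients may be 0 or 1. Live safety oversight is not weakened: 16.42 uses the broader set, the reporting rules in section 10 carry no eligibility condition, and the monitoring board reviews safety data at least twice a year (16.41). All of this stands. It limits the point to the final adverse-event rates and tables.

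Two stronger readings are tempting, and the documents support neither.

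- *Reported toxicity will be understated.* That requires excluded patients to have a higher event rate than the rest. Some eligibility limits concern cardiac, liver or renal function, but 13.4 covers failure of any criterion, including the timing of laboratory tests or prior therapy. The documents give no event rate for such patients, and the table above shows that the rate can also rise.
- *Late ineligibility findings can remove non-responders and inflate the false-positive rate.* If two non-responders were dropped and replaced, the bound would be P(X ≥ 5 | n = 26, 0.10) = 0.1118 instead of 0.0851. But 13.4 ties ineligibility to the facts at registration. The finding may come late, yet the plan does not allow it to depend on response. The 0.1118 would need outcome-driven exclusions and is not a property of this design.

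**Conclusion.** The point holds for safety reporting only. Section 16.325 excludes exposed patients from the rates that answer goal 2.24, 13.4 foresees such patients and requires their data, and 16.42 does not apply the restriction.

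If the allowance in 16.22 is taken as the limit, at most about 2 of 26 patients (7.7%) are affected, and none if no treated patient is found ineligible. In the illustration with 6 events among 26, the distortion runs from 6.4 percentage points too low (23.1 − 16.7) to 1.9 too high (25.0 − 23.1). Both differences are well within the sampling uncertainty of a trial this size. The more practical risk is that an event confined to the excluded patients goes unlisted. The response analysis needs no change on this ground.

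**What to change.** In 16.325, define the adverse-event population as all patients who received at least one dose of either study drug, regardless of any later eligibility finding, using data up to the point to which 13.4 requires them. State in 16.42 that both limbs of the stopping rule use this same population, which also settles what the second limb means by all patients. Leave the eligible, treated set in place for the 24-patient response rule.

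The cost is a change of wording. Sample size, cut-off, significance level (0.085) and power (0.889) stay as they are, and no new data are needed. There are two drawbacks to accept. Adverse-event rates may look slightly less favourable. Observation of ineligible patients is also cut short: 13.4 requires their data only up to confirmation of ineligibility, and the follow-up table in 18.1 then lists only the event monitoring form. A footnote to the adverse-event table should give the number of such patients and say that their follow-up is truncated.
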